8.2.5 Clinical safety laboratory tests

• See Appendix 2 (Section 10.2) for the list of clinical laboratory tests to be performed and to the SoA (Section 1.3) for the timing and frequency. These tests will be done at each cycle; during the first 2 cycles, hematology, and liver function tests (ie, alanine aminotransferase [ALT], aspartate aminotransferase [AST], alkaline phosphatase [ALP], total and direct bilirubin) will be assessed weekly.

- If Grade 4 neutropenia occurs, assess absolute neutrophil count (ANC) every 2 to 3 days until ANC ≥0.5 × 10⁹/L.
- In case of Grade ≥3 abnormal liver function tests, additional tests will be done every 2 to 3 days until recovery to the baseline value. Additional tests will be performed when clinically appropriate. This test can be performed before the study intervention administration on the same day or the day before.
- The Investigator must review the laboratory report, document this review, and record any clinically significant changes occurring during the study as an AE. The laboratory reports must be filed with the source documents. Abnormal laboratory findings associated with the underlying disease are not considered clinically significant, unless judged by the Investigator to be more severe than expected for the participant's condition.
- All laboratory tests with values considered clinically significantly abnormal during participation in the study or within 30 days after the last dose of study intervention should be repeated until the values return to normal or baseline or are no longer considered clinically significant by the Investigator.
 - If clinically significant values do not return to normal/baseline within a period of time judged reasonable by the Investigator, the etiology should be identified and the Sponsor notified.
 - All protocol-required laboratory tests, as defined in Appendix 2 (Section 10.2), must be conducted in accordance with the laboratory manual and the SoA (Section 1.3).
 - If laboratory values from non-protocol specified laboratory tests performed at the institution's local laboratory require a change in participant management or are considered clinically significant by the Investigator (eg, SAE or AE or dose modification), then the results must be recorded.

8.2.6 Guidelines for management of adverse events

Management of AEs related to tusamitamab ravtansine is summarized in Appendix 6 (Section 10.6).

8.2.6.1 Hypersensitivity reactions

Premedication treatments provided as prophylactic treatment for hypersensitivity reactions are detailed in Section 6.1.

In case of event of hypersensitivity reactions, please refer to the recommended dose modification or discontinuation Table 10 (Section 10.6).

8.2.6.2 Ocular toxicity

• It is recommended that topical artificial tears (and/or hyaluronic ophthalmic gel) are used regularly in all patients treated with tusamitamab ravtansine during the study treatment period.

- The patient should be asked about ocular/visual symptoms at each visit, and ocular evaluation including visual acuity, slit lamp examination under dilatation, and Schirmer's test should be carried out on according to SoA (Section 1.3). Ocular evaluation will be performed at screening, as required during the treatment (ie, on occurrence of ocular symptoms such as blurred vision, photophobia, pain), at the EOT visit, and when relevant at follow-up visit(s). The outcome of the examination should be available before infusion of the next cycle. If ocular symptoms are present, then a formal ocular examination should be performed. In patients with any ocular/visual symptom(s) (eg, blurred vision, photophobia), the ocular evaluation should be repeated once weekly, unless less frequent assessment is recommended by an ophthalmologist, until resolution to Grade 1. Subsequently, the participant should be followed with ocular exam (slit lamp and visual acuity) at each cycle until total resolution of the event.
- Photographs of the cornea are recommended to be taken at the site, if possible, when ocular findings are first documented, and to follow progression when relevant. Tonometry and additional ocular assessment can be performed at the discretion of an ophthalmologist when applicable.

8.2.6.3 Keratopathy/keratitis management

- Reversible non-inflammatory, microcystic keratopathy was identified as the dose limiting toxicity (DLT) during the dose escalation process in study TED13751with tusamitamab ravtansine. At slit-lamp examination, it presents as lesions consisting of 100s to 1000s microcysts and/or deposits that are initially observed at the periphery of the cornea, the limbus being preserved. The lesions have a centripetal distribution and evolve towards the center of the corneal upon resolution, following the natural keratinocyte regeneration process.
- For standardization of AE verbatim, keratopathy should be the preferred term unless otherwise specified by an ophthalmologist due to inflammatory findings on eye exams leading to a diagnosis of keratitis.
- The potential ocular/visual toxicity symptoms could include, but are not limited to, blurred vision, dry eye, and photophobia. Curative treatment may be used as recommended by an ophthalmologist.
- No primary prophylaxis other than prevention of dry eye with artificial tears and/or hyaluronic ophthalmic gel is recommended; the use of contact lenses is not permitted during the treatment period. Corticosteroid-containing ocular drugs are recommended for the management of keratopathy/keratitis in the case that ocular symptoms occur, and treatment will be performed based on discretion of ophthalmologist. Dose modification and recommendations are further described in Appendix 6 (Section 10.6).
- After resuming study treatment, a patient who had Grade ≥2 keratopathy/keratitis should be followed with standard ocular exams (ie, slit lamp examination under dilatation and visual acuity) every 2 cycles, even if symptoms are no longer reported. If no event recurs during the next 4 cycles, then regular follow-up (ie, symptom assessment at each visit with standard ocular exam in case of any ocular sign/symptom) is applied.

8.2.6.4 Management of anemia

Close surveillance of any signs and symptoms is required: a routine blood hematology workup, including red blood cells (RBC) counts, hemoglobin, hematocrit, white blood cells (WBC) with differential, and platelet counts will be done weekly during the first 2 cycles, and thereafter each treatment cycle before IMP administration. Patients should not start Cycle 1 treatment if hemoglobin is <9.0 g/dL. To be eligible for the study and to receive the first study treatment, the participant must have been transfusion-free for 2 weeks. During the treatment period, erythrocyte transfusion can be given, upon Investigator decision. Erythropoietin can be given at the discretion of the Investigator, except during screening and the first 2 cycles. Cycle delays or modifications should be compliant with Appendix 6 (Section 10.6).

8.2.6.5 Management of neutropenia

- In patients who experienced either Grade 3 or 4 febrile neutropenia or Grade 4 decreased neutrophil count (<500 cells/mm³) for more than 1 week during study intervention, prophylactic Granulocyte colony-stimulating factor (G-CSF) should be implemented per American Society of Clinical Oncology (ASCO) guidelines (20) to ensure dose intensity (Appendix 6, (Section 10.6). Doses of tusamitamab ravtansine should be reduced in case of recurrent events even after prophylactic G-CSF use.
- If the patient continues to experience these reactions at a lowered dose, the treatment should be discontinued (Section 7.1).

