	Grade 4 Perforation, best corrected visual acuity of 20/200 or worse in the affected eye	Definitive discontinuation of SAR408701.	Complete the corneal examination as recommended by ophthalmologist. Repeat the standard ocular examination weekly ^c until resolution. Start curative treatment per ophthalmologist recommendation.
Conduction disorder associated with SAR408701	Grade 1 Mild symptoms	SAR408701 administration to be continued upon decision by the Investigator and Sponsor, depending on the nature of the conduction disorder.	ECG performed once weekly until event resolution. Additional evaluations such as LVEF and Holter monitoring should be performed when relevant.
	Grade ≥2	Definitive discontinuation of SAR408701.	ECG to be repeated twice weekly until event resolution. Prompt cardiology consultation Additional evaluations such as LVEF and Holter monitoring should be performed when relevant.
Neutrophil count decreased	Grade 1 <lln-1500 mm³;
<lln-1.5 109/L</lln-1.5></lln-1500>	No change in IMPs administration.	No intervention.

Event	Symptoms severity (NCI-CTCAE v5.0)	Dose modification	Supportive care guidelines
	Grade 2 <1500-1000/mm³; <1.5-1.0 × 10 ⁹ /L	Delay the cycle until recovery of ANC >1500/mm ³ . Restart at the same dose.	No intervention.
	Grade 3 <1000-500/mm ³ ; <1.0-0.5 × 10 ⁹ /L Or Grade 4 <500/mm ³ ; <0.5 × 10 ⁹ /L	Delay the cycle. Restart the treatment when ANC >1500/mm ³ at the same dose. Prophylactic G-CSF can be considered in all subsequent cycles	Follow ASCO guidelines on usage G-CSF and antibiotherapy (20). Repeat the test every 3 days.
	Grade 4 >7 days <500/mm ³ ; <0.5 × 10 ⁹ /L	Delay the cycle until ANC >1500/mm ³ . 1st episode: administer next cycle at the same dose and administer growth factors 2nd episode: administer SAR408701 at reduced dose 3rd episode: definitive discontinuation	Follow ASCO guidelines on usage G-CSF and antibiotherapy (20). Repeat the test every 3 days.

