Febrile neutropenia	Grade 3 Absolute neutrophil count <1000/mm ³ with a single temperature of >38.3°C (101°F) or a sustained temperature of \geq 38°C (100.4°F) for more than 1 hour	Delay cycle until ANC >1500/mm ³ . 1st episode: administer next cycle at the same dose and administer G-CSF 2nd episode: administer SAR408701 at reduced dose 3rd episode: definitive discontinuation	To ensure relative dose intensity, G-CSF is recommended as secondary prophylaxis in all participants with Grade ≥3 febrile neutropenia ASCO guideline is recommended for supportive treatment if there are no defined clinical standards (20).
	Grade 4 Life-threatening consequences	Administration changes to be decided at the Investigator's discretion. 1st episode: administer next cycle at reduced dose and administer G-CSF or definitively discontinue 2nd episode: definitive discontinuation	
Hepatic enzyme increase	Grade 1-2	Administer SAR408701 as planned.	No intervention.
	Grade 3	Delay the cycle. Restart the treatment until recovery to Grade 1.	Additional liver function tests will be done every 2-3 days until recovery to baseline value.
	Grade 4	SAR408701 should be permanently discontinued.	Additional liver function tests will be done every 2-3 days until recovery to baseline value.
Peripheral neuropathy	Grade 1 Asymptomatic	No action	Participant who has ongoing grade 1 neuropathy has high risk of

Clinical Trial Protocol SAR408701-ACT17241 - tusamitamab ravtansine 27-Sep-2021 Version number: 1

Event	Symptoms severity (NCI-CTCAE v5.0)	Dose modification	Supportive care guidelines
	Grade 2 Moderate symptoms; limiting instrumental Activities of Daily Living	Delay cycle, dose reduction if no improvement with dose delay	worsening of his/her symptoms and should be closely followed.
	Grade 3 Severe symptoms; limiting self-care Activities of Daily Living	Definitive discontinuation	-
	Grade 4 Life-threatening consequences; urgent	Definitive discontinuation	-

ASCO = American Society of Clinical Oncology; BSA = Body surface area; ECG = Electrocardiogram; G-CSF = Granulocyte colony-stimulating factor; IMP = Investigational medicinal product; IV = Intravenous; LLN = Lower limit of normal; LVEF = Left ventricular ejection fraction; NCI-CTCAE = National Cancer Institute Common Terminology Criteria for Adverse Events; and RBC = Red blood cell.

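### Protocol Section 8.2.6.5 lists Grade 4 febrile neutropenia under a reduce-on-recurrence ladder, while Table 10 gives that event a stricter row: a low-priority safety wording inconsistency

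*Protocol*

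**What the plan says.** Section 8.2.6.5 of the protocol opens by naming its events together: "In patients who experienced either Grade 3 or 4 febrile neutropenia or Grade 4 decreased neutrophil count", the last of these lasting more than one week. For all three it calls for prophylactic G-CSF, with dose intensity as the aim and a pointer to Appendix 6. It continues: "Doses of tusamitamab ravtansine should be reduced in case of recurrent events even after prophylactic G-CSF use". The second bullet closes the sequence: "If the patient continues to experience these reactions at a lowered dose, the treatment should be discontinued".

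Table 10 (Appendix 6, Section 10.6) treats the three events in separate rows:

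- Grade 3 febrile neutropenia begins with "1st episode: administer next cycle at the same dose and administer G-CSF", then a reduced dose at the second episode and discontinuation at the third.
- Grade 4 neutrophil decrease beyond 7 days begins with "1st episode: administer next cycle at the same dose and administer growth factors", followed by the same two steps.
- Grade 4 febrile neutropenia, which the table defines by life-threatening consequences, opens with "Administration changes to be decided at the Investigator's discretion" and then lists: "1st episode: administer next cycle at reduced dose and administer G-CSF or definitively discontinue 2nd episode: definitive discontinuation".

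Section 6.5 says that dose modifications for toxicity follow Appendix 6, and Section 8.2.6 refers to the same appendix for adverse event management. Table 6 gives the full dose as 100 mg/m² and the reduced dose as 80 mg/m², both every 2 weeks.

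**The concern.** The narrative section and the table do not give the same sequence for the most severe of the three events. Section 8.2.6.5 ties the first step to G-CSF and keeps dose reduction for recurrence. A site that worked from that section alone could therefore resume at the full dose after a first life-threatening febrile neutropenia, and then reduce instead of stop after a second. Table 10 lists neither course for this event.

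The matter is participant safety and clarity for sites. Section 6.5 asks for Sponsor consultation when a dose change departs from what the protocol states; with two stated sequences, it is less clear what counts as a departure.

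**Working it through.** No stated figure is in dispute, so the check is a comparison of texts.

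**Step 1: compare the three events.**

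| Event | Section 8.2.6.5 | Table 10 | Agree? |
|---|---|---|---|
| Grade 3 febrile neutropenia | G-CSF; reduce on recurrence; stop if it continues at the lowered dose | Same dose with G-CSF; reduced dose; stop | Yes |
| Grade 4 neutrophil decrease, more than 7 days | As above | Same dose with growth factors; reduced dose; stop | Yes |
| Grade 4 febrile neutropenia | As above | Reduced dose with G-CSF, or stop; then stop | No |

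The shared ladder fits two of the three events.

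**Step 2: first Grade 4 febrile episode.** Section 8.2.6.5 requires G-CSF and names no dose. It does not say that the next cycle is at the same dose, and it does not forbid an earlier reduction. A site that gives G-CSF and 80 mg/m² satisfies both texts. The difference is by implication only: reduction is mentioned for recurrence and not before.

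**Step 3: second Grade 4 febrile episode.** The answer depends on what was done after the first.

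- Dose reduced to 80 mg/m² after episode 1: the second bullet of Section 8.2.6.5 leads to stopping, and so does Table 10. The texts agree.
- Treatment stopped after episode 1: no second on-treatment episode arises.
- Resumed at 100 mg/m² after episode 1: Section 8.2.6.5 leads to reduction, Table 10 to stopping. The texts differ.

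**Step 4: size for one participant.** On the third path the dose after episode 1 is 100/80 = 1.25 times the Table 10 reduced dose, that is, 25% higher. Stopping comes after the third episode, against the first or second under Table 10.

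**Step 5: how often the event might occur.** The documents give no Grade 4 rate.

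- Table 1 reports 4 patients (3.3%) with serious febrile neutropenia in EFC15858, Grades 3 and 4 combined, with no treatment arm stated. A count of 4 rounds to 3.3% for a denominator of 120 to 123. Taking 121, 38 × 4/121 = 1.26 participants for both grades together.
- If k of those 4 were Grade 4 (an assumption), 38 × k/121 gives 0, 0.31, 0.63, 0.94 and 1.26 for k = 0 to 4.
- For the pool treated at 100 mg/m² every 2 weeks in TED13751, Table 1 gives 5 patients (2.7%) with Grade 3 or higher events in the whole blood and lymphatic class. If febrile neutropenia is coded there (an assumption), 38 × 5/186 = 1.02 for all events in that class.

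These are point estimates of events, not bounds, and not counts of misdosed participants.

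**The case against.** The strongest reply is that the protocol already settles the matter. Section 6.5 assigns dose modification to Appendix 6, Section 8.2.6 repeats the pointer, and the G-CSF sentence in Section 8.2.6.5 cites the appendix itself. That sentence is about G-CSF, not dose, and it parallels the supportive-care column of Table 10, which also takes the two grades together: "G-CSF is recommended as secondary prophylaxis in all participants with Grade ≥3 febrile neutropenia". The Grade 4 row leaves room for the Investigator's judgement, Section 6.5.1 sets recovery criteria before any re-dosing, and Section 7.1.1 provides for stopping after an unacceptable adverse event.

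Most of this stands, and it is why the point is small. Four things limit it:

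- The reduction sentence in Section 8.2.6.5 carries no pointer to Appendix 6. The stopping bullet points to Section 7.1, which has no rule for febrile neutropenia. The neighbouring sections on anemia and neuropathy tie dose changes to Appendix 6 expressly; this one does not.
- The rule in Section 6.5 that the most conservative adjustment prevails is written for a participant with several reactions, not for two texts on one event. The same section also urges keeping the full dose and dose intensity.
- The retreatment criteria decide whether to re-dose, not at what dose.
- After the reference to discretion, the Grade 4 row lists only reduction or stopping.

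A reader might infer that Section 8.2.6.5 orders full-dose retreatment after a life-threatening event, or that the two texts clash at both episodes whatever was done first. Neither is supported: the section states no first-episode dose, and the second-episode clash disappears once the dose has been reduced.

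**Conclusion.** This is an internal inconsistency in safety wording, of low priority. Section 8.2.6.5 includes Grade 4 febrile neutropenia in a ladder that Table 10 does not give it. The difference is implied at the first episode and conditional at the second. Table 10 is best read as governing, although no sentence says in terms that it takes precedence, so a site that follows the cross-references reaches the stricter row.

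The comparison of texts is firm. The frequency is not: it rests on a rate for Grades 3 and 4 combined from another study. A reader might want to turn the event figures into a number of misdosed participants. The documents do not allow it, because they say nothing about how many would resume treatment or how many sites would use Section 8.2.6.5 without Table 10. Nor is there a statistical consequence: the response rate analysis, the interim rule and the sample size do not depend on this wording.

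**What to change.** In Section 8.2.6.5:

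- Limit the reduce-on-recurrence ladder to Grade 3 febrile neutropenia and Grade 4 neutrophil count decrease lasting more than 7 days.
- Keep secondary G-CSF for all febrile neutropenia of Grade 3 or higher when treatment resumes, in line with Table 10.
- Add one sentence: Grade 4 febrile neutropenia is managed per the Grade 4 row of Table 10, which takes precedence.

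The cost is wording in one section. Visits, data collection and analyses are unchanged, and the edit can go into the next amendment or a clarification to sites.

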8.2.6.6 Liver function tests

- Hepatic enzyme increase has been reported with tusamitamab ravtansine administration. Patients should be carefully followed and in case of Grade ≥3 abnormal liver function tests, additional liver function tests will be done every 2 to 3 days until recovery to baseline value. Tusamitamab ravtansine should be permanently discontinued in case of drug-induced Grade 4 liver enzyme increase.
- Grade \geq 3 (ie, >5 × ULN) increased liver enzyme events should be reported as AESIs.

8.2.6.7 Peripheral neuropathy

- Participants with a known history of peripheral neuropathies and/or patients having received medications known to cause peripheral neuropathies (eg, prior antitubulin, platinum and/or taxanes) are at high risk of developing neuropathy. Peripheral neuropathies potentially present as signs and symptoms of sensory (paresthesia, dysesthesias, pain, and change in proprioception), motor (weakness), and neural dysfunctions.
- There is no further recommendation beyond routine guidance on prevention and treatment of peripheral neuropathy. Cycle delays or modifications should be compliant with Appendix 6 (Section 10.6).

8.2.6.8 Colitis (including hemorrhagic)

In study TED13751 evaluating tusamitamab ravtansine in patients with several cancer types, a limited number of participants developed colitis. Based on clinical observations, patients with known underlying colitis or gastrointestinal tract conditions are noted to be at highest risk for such events. The monitoring of patients for gastrointestinal toxicities will rely on careful evaluation by routine history, physical examination, and standard laboratory examination. Close surveillance of any signs and symptoms is required, with additional routine hematology workup (hemoglobin, hematocrit, and WBC with differential and platelet counts) whenever indicated. As 1 Grade 4 case of colitis erosive has been reported, it is recommended to conduct close surveillance of any diarrhea event, with further exams when clinically indicated. Treatment is per patient condition, based on Investigator discretion.

8.2.7 Pregnancy testing

Refer to Section 5.1 for pregnancy testing criteria. The Investigator is responsible for review of medical history, menstrual history, and recent sexual activity to decrease the risk of including a female participant with an early undetected pregnancy.

- Pregnancy testing (urine or serum as required by local regulations) should be conducted every 4 weeks during intervention (at study visits and if needed, at home in between visits) as described in Section 1.3.
- Pregnancy testing (urine or serum as required by local regulations) must be conducted corresponding with the time frame for female participant contraception.
- Additional serum or urine pregnancy tests may be performed, as determined necessary by the Investigator or required by local regulation, to establish the absence of pregnancy at any time during the subject's participation in the study.

8.3 ADVERSE EVENTS (AES), SERIOUS ADVERSE EVENTS (SAES) AND OTHER SAFETY REPORTING

The definitions of AEs and SAEs can be found in Appendix 3 (Section 10.3). The definition of AESI is provided in Section 8.3.7.

The Investigator and any qualified designees are responsible for detecting, documenting, and recording events reported by the participant (or, when appropriate, by a caregiver, surrogate, or the participant's legally authorized representative) that meet the definition of an AE or SAE and remain responsible for following up AEs that are serious, considered related to the study intervention or study procedures, or that caused the participant to discontinue the study intervention (see Section 7).

The method of recording, evaluating, and assessing causality of AEs and SAEs and the procedures for completing and transmitting SAE reports are provided in Appendix 3 (Section 10.3).

